4. To evaluate the cellular immune stimulatory efficacy, persistence, and duration of prophylactic hAd5-S-Fusion+N-ETSD cellular immunity against confirmed SARS-CoV-2 in subjects with serological or virological evidence of infection before vaccination	Memory immune CD4 ⁺ and CD8 ⁺ T cell stimulation from baseline to specific times during the study, as noted in the Schedule of Events	
 • SARS-CoV-2 specific memory CD4⁺ and CD8⁺ T-cell stimulation to N and S proteins based on central laboratory or locally confirmed NAAT in subjects with serological or virological evidence of SARS-CoV-2 infection
5. To describe the safety, immunogenicity, and efficacy of prophylactic hAd5-S-Fusion+N-ETSD in individuals with confirmed stable HIV disease		
 • All safety, immunogenicity, and efficacy endpoints described above

^a HIV-positive and participants who develop immunosuppressive related diseases (eg, cancer, autoimmune disease) in Phase 3 will not be included in analyses of the objectives, with the exception of the specific exploratory objective.
		

Study Design:
 
This is a phase 2/3, multicenter, randomized, placebo-controlled, observer-blind study assessing the safety, tolerability, immunogenicity, and efficacy of prophylactic hAd5-S-Fusion+N-ETSD against COVID-19. The study schema is shown in Figure 1. Subjects will be ≥ 16 years of age who are healthy or have medically-stable chronic diseases and are at increased risk for SARS-CoV-2 infection and COVID-19. Approximately 20,700 subjects will be randomized in a 1:1 ratio to receive 2 subcutaneous (SC) doses of either 1×10^{11} viral particles (VP)/dose hAd5-S-Fusion+N-ETSD or placebo 3 weeks apart, on Days 1 and 22. Randomization will be stratified by age (16 to 55 years or >55 years). It is intended that a minimum of 25% of subjects will be in the >55-year stratum. Safety, immunogenicity, and efficacy assessments will be conducted per the Schedule of Events (SoE) and subjects are expected to participate for up to a maximum of approximately 2 years.
 
The first 200 subjects randomized will comprise the phase 2 portion of the study. Safety data through 7 days after Dose 2 from these 200 subjects will be analyzed by an independent statistical team and reviewed by the DMC. Enrollment may continue during this period and these subjects would be included in the phase 3 portion of the study.
		

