The secondary primary endpoint is COVID-19 incidence based on central laboratory or locally confirmed NAAT in subjects with and without evidence of infection before vaccination.

Immunogenicity: Humoral immune response will be evaluated by S-binding IgG levels, N-binding IgG levels, and SARS-CoV-2 neutralizing antibody by cPass assay. Cellular immune response will be evaluated by SARS-CoV-2 specific memory CD4⁺ and CD8⁺ T-cell stimulation to N and S proteins.

Statistical Methods:

Primary Efficacy Endpoints: The first primary efficacy endpoint is COVID-19 incidence based on central laboratory or locally confirmed NAAT in subjects with no serological or virological evidence (up to 14 days after receipt of the last dose) of past SARS-CoV-2 infection and will be summarized in terms of $VE = 100\% \times (1 - IRR)$ [ratio of active vaccine to placebo].

After the above first primary endpoint is met, the second primary endpoint will be evaluated.

The second primary endpoint COVID-19 incidence based on central laboratory or locally confirmed NAAT in subjects with and without evidence of infection before vaccination.

Sample Size: The first 200 subjects randomized in the study will be included in phase 2. Phase 2 subjects will be included in the phase 3 portion of the study.

For phase 3, ~20,700 subjects will be randomized in a 1:1 ratio to either the hAd5-S-Fusion+N-ETSD or placebo. All randomized subjects who received at least one dose of study intervention will be included in the all-available efficacy population. The primary efficacy analysis will be based on the evaluable efficacy population which will include subjects in the all-available efficacy population who receive all planned doses of vaccine per schedule and have no major protocol deviations judged to effect efficacy.

The phase 3 sample size calculation is based on the primary efficacy endpoints and derived from the exact conditional test under the Poisson assumption which is appropriate for large trials where the illness rate is very low and hypothesis testing is based on a non-zero lower bound ([Chan 1998](#)). The null and alternative hypotheses for the primary efficacy analyses are:

Ho: $VE \leq 30\%$

Ha: $VE > 30\%$

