Under the assumption that the true VE is 60%, the primary efficacy analysis will require ~160 confirmed COVID-19 illness cases which will provide 90% power to conclude the true VE is $> 30\%$. Assuming the placebo illness rate is 1.3%, ~17,600 subjects will be required in the evaluable efficacy population for the primary efficacy analyses. These calculations are based a one-sided Type I error rate of 0.025. Assuming 15% of the all-available efficacy population will be unevaluable for the evaluable efficacy population, ~20,700 subjects will be sufficient to accrue ~17,600 subjects in the evaluable efficacy population.

Dependent upon the evolution of the pandemic, it is possible that the COVID-19 illness rate may change as the study progresses. An increase in illness rate could accelerate case accrual allowing the primary endpoints to be evaluated sooner, whereas a decrease in illness rate could slow down case accrual delaying the evaluation. At the time of the first interim efficacy analysis, the independent statistical team and DMC will evaluate the placebo illness rate. If the upper bound of the two-sided 95% CI for the observed placebo illness rate is less than the assumed placebo illness rate, then the sample size will be re-estimated by the independent statistician and DMC based on the observed placebo illness rate, and recommendations made to the Sponsor for final decision by the Sponsor.

Primary Efficacy Analysis: The primary efficacy endpoints will be analyzed at 2 interim analyses and the final analysis. The interim analyses will be conducted by the independent statistical team and reviewed by the independent DMC. The Lan-DeMets/O'Brien-Fleming alpha(α)-spending function ([Lan 1983, O'Brien 1979](#)) will be used to control the overall Type I error at one-sided 0.025 level. At each analysis, VE will be summarized by the one-sided $(1-\alpha)100\%$ CI. The table below summarizes the

information fraction (ie, % of total cases), nominal α , criterion for success, and cumulative probability of success if the true VE is 60% for each analysis:

Analysis	Information Fraction (% of Total Cases)	α	Success Criterion	Cumulative Probability of Success (if true VE=60%)
Interim #1	40% (64 cases)	0.0004	Point estimate of VE \geq 50% and lower bound of the one-sided 99.96% CI for VE is $>$ 30%	9.9%
Interim #2	70% (112 cases)	0.0073	Point estimate of VE \geq 50% and lower bound of the one-sided 99.27% CI for VE is $>$ 30%	61.5%

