Final	100% (160 cases)	0.0227	Point estimate of VE \geq 50% and lower bound of the one-sided 97.73% CI for VE is $>$ 30%	90.0%

Should the primary endpoint(s) show success at either interim analysis, the Sponsor will decide after discussion with FDA to explore the options to expedite submission of the data for approval and possible early closure of the trial, with long-term follow up of patients already enrolled.

The study may be stopped early for futility (lack of benefit) at either interim analysis if the conditional power for the first primary endpoint is less than 5% ([Jennison 2000](#)).

A Poisson regression model with robust error variance will be used to estimate VE and its one-sided $(1-\alpha)100\%$ CI ([Zou 2004](#)).

Safety Analyses: Safety analyses will be based on the safety analysis population and subjects will be analyzed according to the actual study intervention received. Descriptive statistics will be provided for each reactogenicity endpoint for the active vaccine group and the placebo group. Local reactions and systemic events from Day 1 through Day 7 after each vaccination will be presented overall and by severity.

AEs and SAEs will be categorized according to the MedDRA terms. Descriptive statistics will be provided for each AE for the active vaccine group and the placebo group. For phase 2, AEs and SAEs will be presented for first vaccination through 7 days after last vaccination overall and by severity. For phase 3, AEs will be presented for first vaccination through 1 month after last vaccination and SAEs will be presented for first vaccination through 6 months after last vaccination overall and by severity.

Immunogenicity Analyses: Immunogenicity analyses will be based on the immunogenicity analysis population and subjects will be analyzed according to the actual study intervention received. Humoral immune response endpoints will be summarized descriptively for the vaccine and placebo groups by GMT, GMC, GMFR, percentage of subjects with titers greater than defined threshold(s), and neutralizing antibody titer demonstrated by ACE2 inhibition at baseline and specific times during the study, as noted in the Schedule of Events. Cellular immune response endpoints will be summarized

descriptively for the vaccine and placebo groups at baseline and specific times during the study, as noted in the Schedule of Events.

Figure 1: Study Schema

[figure not shown]

Table 8: Schedule of Events

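### Randomization is stratified by age, but no vaccine efficacy (VE) by age stratum is pre-specified, so the trial can succeed with little efficacy in the >55 stratum and no planned analysis would report it

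*Combined protocol and SAP*

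**What the plan says.** Study Design: "Randomization will be stratified by age (16 to 55 years or >55 years"). The same paragraph adds: "It is intended that a minimum of 25% of subjects will be in the >55-year stratum". Age is the only stratification factor named.

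Statistical Methods, Primary Efficacy Analysis: "A Poisson regression model with robust error variance will be used to estimate VE" together with its one-sided interval. The sentence lists no covariates; age is neither included nor excluded. At both interim analyses and at the final analysis, success requires an overall VE estimate of at least 50% and a lower bound above 30%. No condition refers to age.

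Objectives table: the primary and secondary efficacy objectives vary by prior infection status, severity and symptom definition, but not by age. One subgroup does have an efficacy objective, an exploratory one: "To describe the safety, immunogenicity, and efficacy of prophylactic hAd5-S-Fusion+N-ETSD in individuals with confirmed stable HIV disease".

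Sample Size: the design assumes a single true VE of 60% and plans for about "160 confirmed COVID-19 illness cases which will provide 90% power".

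**The concern.** Stratifying by age and setting a recruitment target for the >55 stratum suggests that efficacy in older subjects is of interest. Yet every success criterion uses one pooled VE, which is an average weighted by each stratum's share of placebo cases. High efficacy in 16-55 can offset low efficacy in >55.

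This matters because success at an interim may lead to expedited submission and possible early closure. Age is recorded, so VE by age could be computed afterwards. But an age analysis chosen after unblinding is weak evidence, whichever way it points. The plan specifies an efficacy objective for stable HIV but none for its own stratification factor.

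**Working it through.** **Inputs from the plan.** Allocation 1:1; null VE 30%; design VE 60%; looks at 64, 112 and 160 cases; nominal one-sided alphas 0.0004, 0.0073 and 0.0227; success also needs a VE estimate of at least 50%; placebo illness rate 1.3%; 15% unevaluable.

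**Assumptions, not in the plan.** VE in each stratum, and the >55 share of placebo cases, w. The base case is w = 25%, which follows if 25% of evaluable subjects are >55 and placebo attack rates are equal.

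**1. Reproduce the design.** Given T cases, vaccine cases are binomial with p = (1-VE)/(2-VE): 0.4118 under the null and 0.2857 at VE 60%. Success requires at most 13, 33 or 53 vaccine cases at the three looks. The cumulative success probabilities are 9.0%, 62.9% and 91.5%; the plan states 9.9%, 61.5% and 90.0%. Evaluable N = 2 × 160/(0.013 × 1.4) = 17,582 (stated about 17,600), and 17,600/0.85 = 20,706 (stated about 20,700). The design reproduces.

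**2. Pool the strata.** Overall VE = (1-w) × VE(16-55) + w × VE(>55). With w = 0.25 and VE 75% and 15%: 0.75 × 75 + 0.25 × 15 = 60%, exactly the design value.

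**3. Chance of success by the final analysis, same boundaries, futility stopping not applied.**

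| VE 16-55 | VE >55 | Overall VE | Success |
|---|---|---|---|
| 75% | 15% | 60.0% | 91% |
| 70% | 15% | 56.3% | 80% |
| 65% | 15% | 52.5% | 64% |
| 60% | 15% | 48.8% | 46% |
| 60% | 0% | 45.0% | 31% |

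The result is sensitive to w. For VE 70% and 10%, with 25% of subjects >55, success is 94.3%, 75.2% or 52.4% when the >55 attack rate is 0.5, 1 or 1.5 times that in 16-55. With 40% of subjects >55 and equal attack rates it is 34.5%.

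**4. What stratum estimates would show at 160 cases (w = 0.25).** SE of the log rate ratio = √(1/placebo cases + 1/vaccine cases). At overall VE 60%, placebo cases are 160/1.4 = 114.3, split 85.7 (16-55) and 28.6 (>55).

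- VE 60% in both strata: >55 has 28.6 + 11.4 = 40 cases, SE 0.350, 95% CI about 21% to 80%.
- VE 75% and 15%: >55 has 28.6 + 24.3 = about 53 cases, estimate 15%, CI about -46% to 51%. The 16-55 stratum has 85.7 + 21.4 cases, estimate 75%, CI about 60% to 84%.
- Interaction in the 75%/15% case: ln(0.85/0.25) = 1.224; SE = √(1/28.6 + 1/24.3 + 1/85.7 + 1/21.4) = 0.367; z = 3.34; power at two-sided 5% about 92%.

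**5. At an interim, SEs grow by √(160/T).** With VE 60% throughout, >55 has about 28 cases at 112 (CI about 9% to 82%) and 16 cases at 64 (CI about -18% to 86%). In the 75%/15% case, z falls to 3.34 × √0.7 = 2.79 (power about 80%) and 3.34 × √0.4 = 2.11 (about 56%).

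**6. Effect of an age covariate.** In 1,000 simulated trials for each of five scenarios, with arms balanced within stratum, VE with and without an age term was identical. The SE changed by less than 0.0004 (for example 0.1762 against 0.1761), and pass rates were the same.

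**The case against.** Several objections have force.

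- **The overall criterion already gives some protection.** If VE in 16-55 is only the planned 60%, success falls to about 46% with VE 15% in >55, and to about 31% with VE 0%. A reader might infer that a vaccine weak in older adults passes about 90% of the time. That needs VE in 16-55 near 75%, well above the design value, or few >55 cases. The documents give no VE by age, so the whole range has to be shown.
- **The model sentence is not the cause.** A reader might infer that a missing age term hides a weak >55 result. It does not: a model with an age main effect still gives one pooled VE (step 6). Only stratum estimates or an interaction would show the difference. Nor does the text exclude age; it lists no covariates at all.
- **Age imbalance is a weak argument.** A reader might fear that the 15% loss to the evaluable population unbalances age between arms. A 3-point gap in the >55 share combined with a 2-fold incidence difference moves VE by only about 1 point. With about 8,800 per arm, the chance SD of the gap is √(2 × 0.25 × 0.75/8,800) = 0.65 points even without stratification. Nothing in the documents supports a 3-point gap.
- **The >55 subjects do contribute to the overall VE**, and demographics are collected. It would be wrong to say that the target yields no efficacy information, or that a weak result could never be found. The gap is in pre-specification.
- **The available text may be incomplete.** Appendices 2 to 5 are cited but not included, so the absence of an age analysis is established only for the text at hand.
- **Precision is limited if the trial stops early.** The plan gives a 61.5% chance of success by 112 cases at VE 60%, and the >55 estimate is then wide.

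These points narrow the concern. None supplies a planned efficacy result by age.

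**Conclusion.** The concern holds in a limited form. The available text plans no VE by age stratum although age is the stratification factor, and success rests on overall VE alone. With 25% of placebo cases >55 and VE 15% there, success is about 91% to 46% likely as VE in 16-55 runs from 75% to 60%. No pre-specified analysis would report the low value. These figures depend on assumed stratum VEs and an assumed >55 share of cases.

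The planned case count can support a useful stratum estimate if the trial runs to 160 cases, less so at an interim. Naming the age covariate in the primary model is a separate matter of specification with almost no numerical effect. The change should be made, but the gap does not invalidate the primary test of overall VE.

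**What to change.** 1. Pre-specify, for both primary endpoints, VE with a two-sided 95% CI in each randomization age stratum (16-55 and >55) and a vaccine-by-age interaction test. Label them supportive and outside the alpha plan. Report them at whichever analysis, interim or final, gives the primary result, with the case counts by arm and stratum so that the precision is visible.
2. Separately, state in the model sentence that the primary Poisson regression includes the age stratum as a covariate, so that the analysis matches the randomization. Do not present this as the answer to point 1.

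Cost: a few sentences of SAP wording and one table. The age stratum is already known for every randomized subject, so no new data are needed. No alpha is spent, and the sample size and success criteria do not change.

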1. To define the safety profile of prophylactic hAd5-S-Fusion+N-ETSD in the first 200 subjects randomized (Phase 2)	In subjects receiving at least 1 dose of study intervention (safety analysis population), the percentage of subjects reporting: 
 • Local reactions for up to 7 days following each dose • Systemic events for up to 7 days following each dose • AEs from Dose 1 to 7 days after the last dose • SAEs from Dose 1 to 7 days after the last dose 	
 • Local reactions (pain at the injection site, redness, and swelling) • Systemic events (fever, fatigue, headache, chills, vomiting, diarrhea, new or worsened muscle pain, and new or worsened joint pain) • AEs • SAEs
2. To define the safety profile of prophylactic hAd5-S-Fusion+N-ETSD in all subjects randomized in Phase 2/3	In subjects receiving at least 1 dose of study intervention (safety analysis population), the percentage of subjects reporting: 
 • Local reactions for up to 7 days following each dose • Systemic events for up to 7 days following each dose • AEs from Dose 1 to 1 month after the last dose • SAEs from Dose 1 to 6 months after the last dose 	
 • AEs • SAEs • In a subset of at least 1,000 subjects: 
 ○ Local reactions (pain at the injection site, redness, and swelling) ○ Systemic events (fever, fatigue, headache, chills, vomiting, diarrhea, new or worsened muscle pain, and new or worsened joint pain)
Secondary Efficacy		
1. To evaluate the efficacy of prophylactic hAd5-S-Fusion+N-ETSD against confirmed severe COVID-19 in subjects without serological or virological evidence of infection before vaccination	In subjects complying with the key protocol criteria (evaluable efficacy population) at least 14 days after receipt of the last dose of study intervention: $VE = 100\% \times (1 - IRR) \quad [\text{ratio of active vaccine to placebo}]$	Confirmed NAAT severe COVID-19 incidence in subjects with no serological or virological evidence of past SARS-CoV-2 infection

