Patient Assessment Number	1	2	3	4	5	6	Unplanned	Unplanned
Activity Description	First Vaccination	Second Vaccination	1-Month Follow-up Assessment	6-Month Follow-up Assessment	12-Month Follow-up Assessment	24-Month Follow-Up Assessment	Potential COVID-19 Illness Assessment	Potential COVID-19 Convalescent Assessment
Assessment Window (Days)	Day 1 ^a	19 to 23 Days After Assessment 1	28 to 35 Days After Assessment 2	175 to 189 Days After Assessment 2	350 to 378 Days After Assessment 2	714 to 742 Days After Assessment 2	Optimally Within 3 Days After Potential COVID-19 Illness Onset	28 to 35 Days After Potential COVID-19 Illness Assessment
Informed consent	X							
Assign subject number	X							
Demographics	X							
Medical history	X							
Perform clinical assessment ^b	X							
Measure height/weight	X							
Measure temperature (body)	X	X						
Perform pregnancy test (if appropriate)	X	X						
Confirm use of contraceptives (if appropriate)	X	X	X					
Collect nonstudy vaccine information	X	X	X	X				
Collect prohibited medication use		X	X	X	X	X	X	X
Confirm eligibility	X	X						

Patient Assessment Number	1	2	3	4	5	6	Unplanned	Unplanned
Activity Description	First Vaccination	Second Vaccination	1-Month Follow-up Assessment	6-Month Follow-up Assessment	12-Month Follow-up Assessment	24-Month Follow-Up Assessment	Potential COVID-19 Illness Assessment	Potential COVID-19 Convalescent Assessment
Assessment Window (Days)	Day 1 ^a	19 to 23 Days After Assessment 1	28 to 35 Days After Assessment 2	175 to 189 Days After Assessment 2	350 to 378 Days After Assessment 2	714 to 742 Days After Assessment 2	Optimally Within 3 Days After Potential COVID-19 Illness Onset	28 to 35 Days After Potential COVID-19 Illness Assessment
Review temporary delay criteria	X	X						
Serum sample for SARS-CoV-2 serology testing	X							X
Collect biospecimen (eg, nasal [midturbinate] swab) for SARS-CoV-2 testing	X	X					X	
Obtain randomization number and study intervention allocation	X							
Administer study intervention	X	X						
Assess acute reactions for at least 30 minutes after study intervention administration	X	X						
Explain subject communication methods (including for e-diary completion)	X							

Patient Assessment Number	1	2	3	4	5	6	Unplanned	Unplanned

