Activity Description	First Vaccination	Second Vaccination	1-Month Follow-up Assessment	6-Month Follow-up Assessment	12-Month Follow-up Assessment	24-Month Follow-Up Assessment	Potential COVID-19 Illness Assessment	Potential COVID-19 Convalescent Assessment
Assessment Window (Days)	Day 1 ^a	19 to 23 Days After Assessment 1	28 to 35 Days After Assessment 2	175 to 189 Days After Assessment 2	350 to 378 Days After Assessment 2	714 to 742 Days After Assessment 2	Optimally Within 3 Days After Potential COVID-19 Illness Onset	28 to 35 Days After Potential COVID-19 Illness Assessment
Provide/ensure the subject has a thermometer (all subjects) and measuring device ^c	X	X						
Review reactogenicity e-diary data ^c	↔	↔						
Review ongoing reactogenicity e-diary symptoms ^c		X	X					
Collect AEs and SAEs as appropriate	X	X	X	X ^d	X ^d	X ^d	X	X ^d
Collection of COVID-19-related clinical and laboratory information (including local diagnosis)							X	X

^a The assessment may be conducted across 2 consecutive days; if so, all steps from assessing the inclusion and exclusion criteria onwards must be conducted on the same day.

^b Including, if indicated, a physical examination.

^c Reactogenicity subset subjects only.

^d Any AEs occurring up to 48 hours after the blood draw must be recorded.

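### No by-arm safety summary is planned after 6 months, although AE/SAE collection is marked at months 12 and 24, and footnote d leaves late SAE recording unclear

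*Combined protocol and SAP*

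**What the plan says.** **Analysis.** In the Combined protocol and SAP, Statistical Methods, Safety Analyses, the phase 3 rule for serious events is "SAEs will be presented for first vaccination through 6 months after last vaccination overall and by severity". For all adverse events the window is shorter: "For phase 3, AEs will be presented for first vaccination through 1 month after last vaccination". For the first 200 subjects it is shorter still: "For phase 2, AEs and SAEs will be presented for first vaccination through 7 days after last vaccination overall and by severity".

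**Estimand.** In the objectives table, Primary Safety objective 2 covers all subjects in phase 2/3 and sets the same limit: "SAEs from Dose 1 to 6 months after the last dose".

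**Collection.** Table 8 (Schedule of Events) has a row "Collect AEs and SAEs as appropriate". It is marked at every planned assessment, including those at 6, 12 and 24 months, and at both unplanned assessments. The 6-, 12-, 24-month and convalescent marks carry footnote d: "Any AEs occurring up to 48 hours after the blood draw must be recorded".

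**Duration.** Under Study Design, "subjects are expected to participate for up to a maximum of approximately 2 years". The Primary Efficacy Analysis text adds that, after success at an interim analysis, the trial might close early while enrolled subjects stay in long-term follow-up.

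**The concern.** The schedule keeps asking about adverse events long after the last planned safety summary has closed. If serious events or deaths became unbalanced between the arms in the second half-year or the second year, no pre-specified table would show it. Any comparison would have to be designed after the events were known, which weakens it even when it is purely descriptive. This matters more because the plan relies on long-term follow-up if the trial closes early, yet names no safety output from that follow-up.

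Footnote d adds a second problem. A site reading it narrowly could record only events close to a blood draw at the 6-, 12- and 24-month visits. Late serious events would then be recorded inconsistently, and so would some of those that the 6-month estimand needs.

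**Working it through.** **Inputs**, all from the document:
- Second vaccination: "19 to 23 Days After Assessment 1"; planned for Day 22, so 21 days after Day 1.
- 6-month visit: 175 to 189 days after Assessment 2 (midpoint 182).
- 24-month visit: 714 to 742 days after Assessment 2 (midpoint 728).
- About 20,700 subjects randomized 1:1, so 20,700 / 2 = 10,350 per arm.

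**Step 1: reproduce the stated duration.** Day 1 to the 24-month visit is 21 + 728 = 749 days, and 749 / 365.25 = 2.05 years. The windows give 19 + 714 = 733 to 23 + 742 = 765 days (2.01 to 2.09 years). This agrees with the stated duration of about 2 years.

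**Step 2: share of follow-up after the SAE cut-off.** Share = (24-month day − 6-month day) / total days.
- From the second dose, midpoints: (728 − 182) / 728 = 546 / 728 = 75.0%.
- From Day 1, midpoints: 546 / 749 = 72.9%.
- Extremes of the visit windows, from the second dose: (714 − 189) / 714 = 73.5% to (742 − 175) / 742 = 76.4%.
- Extremes, from Day 1: 525 / 737 = 71.2% to 567 / 761 = 74.5%.
- Taking 6 months as 183 days, from the second dose: 531 / 714 = 74.4% to 559 / 742 = 75.3%.

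**Step 3: person-time per arm, assuming no dropout.**
- Scheduled: 10,350 × 749 / 365.25 = about 21,220 person-years.
- Inside the SAE window: 10,350 × (21 + 182) / 365.25 = about 5,750.
- Outside it: 10,350 × 546 / 365.25 = about 15,470.

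Dropout falls more heavily on late person-time, so the share actually observed outside the window would be lower than 73%.

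**Step 4: is there another planned summary of late safety?**
- The HIV exploratory objective reuses the endpoints already listed and adds no later window.
- Severe COVID-19 is compared by arm, but it is a secondary efficacy endpoint and does not cover other serious events.
- No other by-arm safety summary appears in the text available.

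**Step 5: two readings of footnote d.**
- *Narrow:* only AEs within 48 hours of a blood draw are recorded at the marked visits. The same footnote sits on the 6-month mark, and the estimand needs all SAEs from Dose 1 to 6 months. This reading would therefore undercut the plan's own primary safety window. It also has little to act on, since the rows shown list serum sampling only at the first vaccination and the convalescent assessment.
- *Broad:* the footnote adds a short AE window around any blood draw, and SAEs since the previous visit are recorded as usual. Late SAEs are then recorded, but no planned summary uses them.

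The document does not say which is meant. Under either reading no by-arm summary covers events after 6 months.

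**The case against.** The strongest reply is that nothing here is inconsistent. Estimand and analysis agree exactly, and 6 months after the last dose is a coherent window for serious events. That stands: the 6-month window is not an error, and a longer table is an addition rather than a correction.

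A reader might infer that 18 months of complete SAE data will lie unused in the database. The document does not establish this. The collection row is qualified ("Collect AEs and SAEs as appropriate") and the late marks carry footnote d, so full recording of late SAEs is unsettled.

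A reader might also infer that the trial could conclude nothing about long-term safety. That does not follow. The safety analysis is descriptive and uses no alpha. The text neither promises nor excludes later listings or review of late SAEs by the DMC. What is missing is a pre-specified summary, and that can be said only of the text available, which is a synopsis with a schedule.

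Finally, late comparisons are harder to interpret. Nonstudy vaccine information is marked only at Assessments 1 to 4, ending at month 6, although prohibited medication use is collected to month 24. This objection stands and has to be met in the fix.

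**Conclusion.** The point holds as an inexpensive improvement. In the text available, no by-arm safety summary is planned for about 73% (from Day 1) to 75% (from the second dose) of the roughly 2-year follow-up. That is about 15,470 of 21,220 scheduled person-years per arm. The shares rest only on the visit windows in Table 8; the person-years also assume 10,350 subjects per arm and no dropout. No number of affected SAEs is offered, because the document gives no SAE rate. Separately, footnote d needs clarifying, since its narrow reading conflicts with the 6-month estimand itself.

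**What to change.** 1. Keep the 6-month SAE summary as the primary safety estimand.
2. Add to Safety Analyses a descriptive by-arm summary of all SAEs and deaths recorded from Dose 1 through the last visit, as counts and per person-time.
3. Reconcile footnote d with the AE/SAE row of Table 8, so that it does not restrict the recording of SAEs at the scheduled visits.
4. Extend the nonstudy vaccine item to the existing 12- and 24-month visits, or state beside the new table that outside vaccination after month 6 is not captured by that item.

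**Cost.** One set of descriptive tables, a footnote change, and either one further question at two visits that already exist or a sentence of limitation. If sites have been reading footnote d narrowly, asking about SAEs at the late visits is also some extra work. Alpha, sample size and the number of visits do not change. The late comparison remains descriptive and may be affected by dropout and outside vaccination, and the table should say so.
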